8.3.3. Analysis of Safety Endpoints

Analysis Set

- Summaries and analyses of the primary safety endpoint will be based on the per protocol analysis set. Summaries and analyses of all other safety parameters will include all patients in the Safety Analysis Set.

- Secondary safety endpoint data will be summarized by dose level (pooling patients treated at the MTD from both phases of the study).
- Adverse events and laboratory tests will be summarized for the following study periods: entire study period and by cycle (Cycle 1, Cycle 2 and Cycles beyond 2) in the Safety Analysis Set; the PK lead-in period for those patients receiving at least one dose of axitinib during the 7 day PK lead-in period; and the treatment period starting at C1D1 for patients receiving the combination treatment.

8.3.3.1. Analysis of Primary Endpoint

Dose Limiting Toxicity (DLT) is the primary endpoint of the study. The occurrence of DLTs observed in the dosing cohorts is used to estimate the MTD as described in the protocol. AEs constituting DLTs will be listed per dose level.

DLT-related listings will be produced by dose

- Patient ID.
- Dose and Date at which DLT occurred.
- Time from treatment start to onset of DLT.
- Time to resolution of DLT to Grade 1 or baseline.
- Dose interruption (yes, no).
- Time to resumption of treatment.
- DLT term.
- Action(s) taken due to DLT (stopped temporarily, permanently discontinued, no action taken, etc).

8.3.3.2. Analysis of Secondary Safety Endpoint

Adverse Events

AEs will be graded by the Investigator according to the Common Terminology Criteria for Adverse Events (NCI CTCAE) version 4.03 and coded using the Medical Dictionary for Regulatory Activities (MedDRA). The focus of AE summaries will be on treatment-emergent AEs. The number and percentage of patients who experienced any AE, serious AE (SAE), treatment-related AE, and treatment-related SAE will be summarized according to worst toxicity grades. The summaries will present AEs on the entire study period, separately for the lead-in PK period and by cycle (Cycle 1, Cycle 2 and Cycles beyond 2), as well as for the entire treatment period starting at C1D1 (first dose of MK-3475).

For AE summaries of the treatment period starting at C1D1, treatment-emergent will be defined as an adverse event with an initial onset or increasing severity after the first dose of

MK-3475. For all other AE summaries, treatment-emergent will be defined as an adverse event with an initial onset or increasing severity after the first dose of any study medication (axitinib, in the case of the lead-in PK period).

- An overall summary of AEs will be provided. The number and percentage of patients who experienced any AE, who experienced any SAE, who experienced any treatment-related AE, who experienced any treatment-related SAE, and who discontinued because of an AE will be presented. Treatment-related AEs are those judged by the investigator to be at least possibly related to the study drug (with a cause related to the study drug indicated on the CRF).
- All treatment-emergent AEs will be summarized by MedDRA SOC and preferred term. A summary of AEs by preferred term and maximum CTCAE grade will be presented. A summary of AEs by preferred term and maximum CTCAE grade group (Grade 1-2, Grade 3-4, and Grade 5) will also be presented. Treatment-emergent AEs will also be summarized for each group and pooled across the groups.
- Treatment-related AEs will be summarized by MedDRA SOC and preferred term separately for axitinib, MK-3475 and both. A summary of treatment-related AEs by preferred term and maximum CTCAE grade will be presented. A summary of treatment related AEs by preferred term and maximum CTCAE grade group (Grade 1-2 vs. Grade 3-5) will also be presented. Treatment-related AEs will also be summarized for each group and pooled across the groups.
- Deaths will be summarized by three time periods (on-treatment vs. within 90 days of end of treatment vs. > 90 days after end of treatment) and cause of death. Deaths that occurred within 28 days after the last dose of study treatment are defined as on-treatment deaths. Death data will also be listed.
- Patients who withdraw from study treatment because of an AE will be listed separately for axitinib and MK-3475. Patient discontinuation will be determined from the end of treatment (EOT) evaluation (where reason for termination is “Adverse Event”) and the specific AE(s) will be determined from the AE CRF page (where action taken is “Withdrawn from Treatment”).
- SAEs and treatment-related SAEs will be summarized by MedDRA SOC and preferred term. Patients who experienced a SAE will be listed.

The following analyses will be performed for AEs of special interest (including, but not limited to, hepatic disorders [ALT, AST and bilirubin], thyroid dysfunction [hypo-/hyperthyroidism], diarrhea, colitis and pneumonitis).

- Hy's Law eDISH scatterplot of Maximum ALT vs. Maximum Total Bilirubin on treatment.

- Hy's Law eDISH scatterplot of Maximum AST vs. Maximum Total Bilirubin on treatment.
- The prevalence of AEs of special interest will be summarized by preferred term and maximum CTC severity grade.
- Descriptive statistics will be presented for time to AE onset (days), time to grade 2 and grade 3/4 AE onset.

For all safety analyses, only descriptive methods will be used without any formal statistical test.

Laboratory Tests

The number and percentage of patients who experienced laboratory test abnormalities will be summarized according to worst toxicity grade observed for each lab assay. The analyses will summarize laboratory tests on the entire treatment period, separately for the lead-in PK period and by cycle (Cycle 1, Cycle 2 and Cycles beyond 2), as well as for the entire treatment period starting at C1D1 (first dose of MK-3475) for patients receiving combination therapy.

For laboratory tests without CTC grade definitions, results will be categorized as normal, abnormal or not done.

- **Hematology** – Descriptive statistics will be provided for each test result and for change from baseline by visit. Hematology results will be graded according to the NCI CTCAE Version 4.03. A summary of maximum CTCAE grade as well as shift summary of baseline grade by maximum CTCAE grade, cycle, and dose will be presented. Patients who developed a grade 3 or greater toxicity will also be listed.
- **Biochemistry** - Descriptive statistics will be provided for each parameter result and for change from baseline by visit. Biochemistry results will be graded according to the NCI CTCAE version 4.03. A summary of maximum CTCAE grade as well as shift summary of baseline grade by maximum CTCAE grade, cycle, and dose will be presented. Patients who developed a grade 3 or greater toxicity will also be listed.
- **Urine** - Descriptive statistics will be provided for urine protein and blood results and for change from baseline by visit. Urine protein and blood data will also be listed and patients with urine protein $\geq 2+$ by semiquantitative method (e.g., dipstick) will have their 24 hour urine collection protein levels listed as well. A shift summary of baseline value by maximum value, cycle and dose will be presented for urine protein.
- **Other Laboratory Tests** – Individual patient test results will be listed.

ECOG Performance Status

ECOG performance status data will be summarized with a shift table of the baseline and the worst on study status. Baseline will be defined as the last evaluation within 28 days prior to the first dose of either axitinib or MK-3475, whichever occurs first.

Vital Signs

Summaries and listings will be presented for blood pressure, body weight and pulse rate.

In addition, the baseline and the change from baseline in blood pressure and pulse rate will be summarized using descriptive statistics by visit. Baseline will be defined as the last evaluation within 28 days prior to the first dose of either axitinib or MK-3475, whichever occurs first.

ECG

All ECG measurements obtained during the study will be listed. Single ECG measurements will be obtained at screening and on Cycle 1 Day 1 and End of Treatment/Withdrawal as well as when clinically indicated.

Concomitant Medications and Non-drug Procedure/Treatments

All drug medications will be coded by the World Health Organization (WHO) medical dictionary. Non-drug procedure/treatments will be coded by the MedDRA dictionary. All medications with a start date prior to lead-in D1 (for patients with a lead-in period) or prior to C1D1 (for patients with no lead-in period) are considered previous medication. All ongoing medications at the end of study or medications with a stop date on or after lead-in D1 (for patients with a lead-in period) or prior to C1D1 (for patients with no lead-in period) are considered concomitant medication. If a medication satisfies both the definition of previous and concomitant medication, it will be considered both previous and concomitant medication.

The number of subjects with any concomitant drug/non-drug treatment will be summarized. Listings of prior and concomitant drug/non-drug treatment will be provided separately. If any prior or concurrent surgery or radiation therapy is given, these data will be listed for each patient. Furthermore, follow-up systemic therapy for the primary diagnosis will be summarized by categories of follow-up therapy and will be listed for each patient as appropriate.

Data Safety Monitoring Committee

A Data Safety Monitoring Committee will not be established for the study.

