Discontinuation from MK-3475 may be considered at the investigator's discretion for patients who have attained a confirmed CR, have received at least 24 weeks of treatment with MK-3475, and have received at least two MK-3475 infusions beyond the date the CR was initially declared. Axitinib may be continued in those patients. Patients who then experience radiologic disease progression will be eligible for re-treatment with MK-3475 at the discretion of the investigator if no other cancer treatment was administered other than axitinib since the last dose of MK-3475, the patient still meets the safety parameters listed in the Inclusion/Exclusion criteria, and the trial is still open. Patients will resume MK-3475 therapy at the same dose and schedule in place at the time of discontinuation. MK-3475 treatment will be administered for up to one additional year.

Patients with unacceptable toxicity attributed to one of the two drugs may be eligible for continued treatment with the other drug (after discussion between the Investigator and the Sponsor).

**Tumor assessment:** Anti-tumor activity will be assessed by radiological tumor assessments conducted at baseline, then at 12 weeks and every 6 weeks thereafter, using RECIST version 1.1. In addition, radiological tumor assessments will also be conducted whenever disease progression is suspected (eg, symptomatic deterioration), and at the time of End of Treatment/Withdrawal (if not done in the previous 6 weeks). In determining whether or not the tumor burden has increased or decreased, Investigators should consider all target lesions as well as non-target lesions according to RECIST v 1.1 (see Study Reference Manual).

If radiologic imaging shows PD, tumor assessment should be repeated  $\geq 4$  weeks later in order to confirm PD. Assigned study treatment may be continued at the investigator's discretion while awaiting radiologic confirmation of progression. If repeat imaging does not confirm PD, study treatment may be continued/resumed. Patients that are deemed clinically unstable are not required to have repeat imaging for confirmation of PD and can discontinue treatment immediately.

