### **6.4. Patient Withdrawal**

Patients may withdraw from treatment at any time at their own request, or they may be withdrawn at any time at the discretion of the Investigator or Sponsor for safety (see also the [Withdrawal From the Study Due to Adverse Events](#) and the Patient Withdrawal section) or behavioral reasons, or the inability of the patient to comply with the protocol required schedule of study visits or procedures at a given study investigator site.

Reasons for discontinuation of study treatment may include:

- Confirmed objective disease progression according to RECIST version 1.1. However, patients with disease progression who are continuing to derive clinical benefit from the study treatment will be eligible to continue with single agent axitinib, MK-3475 or axitinib plus MK-3475 provided that the treating physician has determined that the benefit/risk for doing so is favorable;
- Global deterioration of health status requiring discontinuation;
- Unacceptable toxicity. If the unacceptable toxicity is attributed to one of the two study drugs, the Investigator (in discussion with the Sponsor) can continue the study treatment with the other study drug;
- Pregnancy;
- Significant protocol violation (post study start; includes patient noncompliance);
- Lost to follow-up;
- Patient refused further treatment (follow-up permitted by patient);
- Study terminated by Sponsor;
- Death.

Reasons for withdrawal from study follow-up may include:

- Completed study follow-up;
- Study terminated by Sponsor;
- Lost to follow-up;
- Refused further follow-up for survival;
- Death.

If a patient does not return for a scheduled visit, every effort should be made to contact the patient. All attempts to contact the patient and information received during contact attempts must be documented in the patient's medical record. In any circumstance, every effort should be made to document patient outcome, if possible. The Investigator should inquire about the reason for withdrawal, request the patient return all unused investigational product(s), request the patient return for a final visit, if applicable, and follow up with the patient regarding any unresolved AEs.

If the patient withdraws from the study, and also withdraws consent for disclosure of future information, no further evaluations should be performed, and no additional data should be collected. The sponsor may retain and continue to use any data collected before such withdrawal of consent.

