Footnotes for Schedule of Activities
1. During Treatment: All assessments should be performed prior to dosing with study treatment unless otherwise indicated. Acceptable time windows for performing each assessment are described in the column headings.  Patients who permanently discontinue pembrolizumab and continue on axitinib treatment, it is at the discretion of the investigator to follow patients on axitinib monotherapy every 3 weeks + or – 3 days (ie, cycle=21 days) or 6 weeks + or – 3 days (ie, cycle=42 days). All tests and assessments outlined in the schedule of activities must be conducted at that visit.
2. End of Study Treatment/Withdrawal: Obtain these assessments if not completed during the previous two weeks on study.
3. Physical Examination: Includes an examination of major body systems and weight.
4. In Clinic Blood pressure, pulse rate: Blood pressure, and pulse rate should be taken with the patient in the seated position after the patient has been sitting quietly for at least 5 minutes. Two blood pressure readings will be taken at least 1 hour apart at each clinic visit.
5. Home blood pressure monitoring: All patients will receive home blood pressure monitoring devices and blood pressure will be monitored at home. While on axitinib (as single agent or combined with MK 3475) patients will monitor their blood pressure at least twice daily (before taking each dose of axitinib) and blood pressure should be recorded in a patient diary. Patients should be instructed to contact the site immediately for guidance if their systolic blood pressure rises above 150 mm Hg, diastolic blood pressure rises above 100 mm Hg, or if they develop symptoms perceived to be related to elevated blood pressure (eg, headache, visual disturbance) although a different blood pressure threshold for contacting the site may be used according to the Investigator's clinical judgment (see Section 5.2.7.3 ).
6. Hematology, Blood Chemistry, and Coagulation: Required tests are listed in Table 8 . All laboratory tests may be performed per standard of care and when clinically indicated. Dose adjustment may be required (see Section 5.2.7 ).
7. If protein $\geq 2+$ by semiquantitative method (eg, urine dipstick), protein will have to be quantified by 24 hour urine collection. Dose adjustment may be required (see Section 5.2.7.2 ). May be performed also when clinically indicated.

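### If the end-of-treatment reason is recorded once per patient, the SAP's rule for AE discontinuation misses patients who stop one drug for toxicity and continue the other

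*SAP*

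**What the plan says.** SAP 8.3.3.2 (Adverse Events) plans two outputs on discontinuation.

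- **Overall AE summary.** It gives the number and percentage of patients in several categories, the last being those "and who discontinued because of an AE will be presented". The bullet names no data source. It does not say whether stopping either drug counts, or only stopping both.
- **Listing.** "Patients who withdraw from study treatment because of an AE will be listed separately for axitinib and MK-3475". The same bullet then gives the derivation: "Patient discontinuation will be determined from the end of treatment (EOT) evaluation", limited to evaluations where the reason for termination is an adverse event. The AE page enters only afterwards: "the specific AE(s) will be determined from the AE CRF page", where the action taken is withdrawal from treatment.

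The protocol allows the two drugs to end separately. Section 3.1 says: "Patients with unacceptable toxicity attributed to one of the two drugs may be eligible for continued treatment with the other drug". Section 6.4 repeats that the investigator, with the sponsor, "can continue the study treatment with the other study drug". Appendix 6 (footnotes 1 and 14) sets visit intervals for one such group: "Patients who permanently discontinue pembrolizumab and continue on axitinib treatment". The Schedule of Activities and the Appendix 6 schedule each have one End of Treatment/Withdrawal column.

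**The concern.** The listing is promised by drug, but the event that puts a patient on it is an end-of-treatment reason that may exist only once per patient. A patient who loses one drug to toxicity and carries on with the other has not yet ended study treatment. When that patient does end it, the recorded reason may be progression or refusal, and the earlier AE stop would not be picked up.

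The stake is how completely later tolerability is described. The DLT window covers six weeks. Protocol 5.2.7.4 notes that immune-related events can appear months later, and Protocol 3.4 ties the RP2D partly to whether the MTD can be given over the long term. After week 6, permanent loss of a partner drug to toxicity is one of the plainer descriptive measures of that.

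**Working it through.** The plan states no discontinuation figure, so there is nothing to reproduce. The check has four steps.

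**1. Does the plan produce split stops?** Protocol Tables 5 and 6 give different actions on the two drugs for the same event. They are set out here only to show that split stops can occur, not to judge the rules.

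| Event, Grade 3 or 4 | MK-3475 (Table 6) | Axitinib (Table 5) |
|---|---|---|
| AST/ALT rise, with bilirubin and PT/INR below the Table 5 cut-offs | permanently stopped | withheld, restarted one level lower |
| Nephritis or renal failure | permanently stopped | held, resumed one level lower |
| Pneumonitis | permanently stopped | referred to the general non-hematologic rows |

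So yes. Hepatic events and pneumonitis are also among the SAP's AEs of special interest.

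**2. Is the end-of-treatment reason recorded per patient or per drug?** The documents do not settle it.

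- Pointing to per patient: one End of Treatment/Withdrawal column in each schedule. SAP Appendix 1 names separate axitinib and MK-3475 dosing pages but gives the end-of-treatment evaluation no such split.
- Pointing to per drug: the promise of separate listings in the same SAP bullet.

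The AE page's action-taken field is equally undescribed.

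**3. One patient traced under both readings.** MK-3475 is stopped permanently for hepatitis in Cycle 4. Axitinib continues and ends for progression.

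- One reason per patient: the reason is progression, and the patient is not flagged.
- One reason per drug: MK-3475 carries an AE reason, and the patient is listed correctly.

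**4. Size, if there is one reason per patient.** Let

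- N = 60, the approximate total in SAP 8.1.3;
- b = share whose whole regimen ends for an AE, assumed 10%;
- s = share who stop one drug for an AE and continue the other, assumed 0% to 30%;
- q = share of that group whose later end-of-treatment reason is also an AE, from 0 to 1.

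Only N comes from the documents. Then:

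- stopped at least one drug for an AE = N(b + s)
- found by the rule = N(b + s·q)
- missed = N·s·(1 − q)

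For s = 10% and q = 0.5: 60 × 0.20 = 12 in truth, 60 × (0.10 + 0.05) = 9 found, and 60 × 0.10 × 0.5 = 3 missed.

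| s | At least one drug stopped for AE | Found, q = 0 | Missed, q = 0 | Found, q = 0.5 | Missed, q = 0.5 |
|---|---|---|---|---|---|
| 0% | 6 (10%) | 6 (10%) | 0 | 6 (10%) | 0 |
| 5% | 9 (15%) | 6 (10%) | 3 | 7.5 (12.5%) | 1.5 |
| 10% | 12 (20%) | 6 (10%) | 6 | 9 (15%) | 3 |
| 20% | 18 (30%) | 6 (10%) | 12 | 12 (20%) | 6 |
| 30% | 24 (40%) | 6 (10%) | 18 | 15 (25%) | 9 |

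None are missed if q = 1, if s = 0, or if the reason is held per drug. Even at q = 1, a single AE reason would not show which drug it belongs to, so the per-drug listing could still be wrong when the total is right.

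**The case against.** The strongest objection is that the premise is unproven. A visit column says when assessments happen, not how the CRF pages are built. A listing by drug is most naturally fed by a termination reason held by drug, and the trial already keeps separate dosing pages. The SAP also takes discontinuation for its AE-prevalence denominators from another form, the Subject Summary page, so the end-of-treatment evaluation is not the only record. All of this stands, and it is why the point can be made only conditionally.

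Three further objections have force.

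- The end-of-treatment rule is written in the listing bullet. Carrying it over to the overall percentage is plausible but not stated.
- A remedy that relies on action taken per drug assumes a field the documents do not describe either.
- Single-drug toxicity is partly visible elsewhere: exposure and dose modifications by medication (SAP 8.3.1), related AEs by drug (8.3.3.2), and actions taken for DLTs (8.3.3.1). None of these is said to count AE-related permanent stops by drug over the whole treatment period, so they soften the gap without closing it.

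A reader might infer that the dose decision itself is biased. The documents do not support that. DLTs do not use the end-of-treatment reason, and failing the axitinib or MK-3475 dosing minimum in the window because of toxicity is itself a DLT (Protocol 3.1.2). Ongoing safety review draws on individual and summary data (Protocol 9.7), not on this listing.

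**Conclusion.** The point holds in conditional form. As written, the rule does not guarantee the per-drug listing that the SAP promises. If the end-of-treatment reason is recorded once per patient, AE stops of one drug are under-counted whenever the other drug later ends for a different reason. If it is recorded per drug, nothing is lost.

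It would be tempting to say that these stops are missed and tolerability is overstated. The documents do not establish that, because they describe neither the end-of-treatment form nor the action-taken field. The size is unknown and its range begins at zero. The counts in the table rest on assumed values of b, s and q.

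The affected outputs are descriptive and secondary: the per-drug listing, and the overall percentage if it follows the same rule. One ambiguity remains on either reading: the SAP does not say whether that percentage means either drug, both drugs or the whole regimen, so two programmers could report different figures from the same data.

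**What to change.** In SAP 8.3.3.2:

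- Derive permanent AE discontinuation separately for axitinib and MK-3475 from that drug's dosing record together with the AE page's action taken, or from a drug-specific end-of-treatment reason if one exists, whatever the whole-regimen reason says.
- Report four counts: axitinib, MK-3475, either drug, both drugs.
- State which count the overall AE summary uses, and its source.

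Before this is programmed, the sponsor should confirm that action taken can be attributed to each drug. If it cannot, the SAP should say how attribution will be made.

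The cost is SAP wording and a small programming change, with no new visits. The reported discontinuation rate may rise. If the end-of-treatment reason is already held per drug, the listing needs only clearer wording, and the overall percentage still needs a definition.

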Pharmacokinetic assessment: MK-3475 and axitinib do not have competing elimination/metabolism pathways, hence an overt PK interaction between the two drugs is not anticipated. However, pharmacokinetic assessments will be conducted in this study to confirm the absence of drug-drug interactions. To understand the PK effects of MK-3475 on axitinib, a 7-day lead-in period of single-agent axitinib will be included prior to Cycle 1 in all patients in the Dose Finding Phase and in at least 8 patients in the Dose Expansion Phase of the study. Axitinib has a plasma half life of 2.5-4.1 hours and is expected to reach steady-state within 2 to 3 days of dosing. MK-3475 has a long plasma half-life (21-28 days) and trough concentrations increase with successive doses until steady state, which is expected within 5 months of MK-3475 dosing. The administration of single agent MK-3475 to this patient population is not considered in this trial. Therefore, the effect of axitinib on MK-3475 will be evaluated by comparing MK-3475 pharmacokinetics at steady-state in the presence of axitinib with those reported for MK-3475 alone in prior studies. At least 8 patients (target is 8 PK evaluable patients) from the Dose Expansion Phase will participate in PK assessments, therefore these patients will undergo the 7-day lead-in period for axitinib. There will be no lead-in period for the remaining patients in the Dose Expansion Phase.

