#### **5.4. Concomitant Medication(s)**

Concomitant treatment considered necessary for the patient's well being may be given at discretion of the treating physician.

Concomitant medications and treatments, including herbal supplements, will be recorded from 28 days prior to the start of study treatment and up to 28 days post the last dose of study treatment. All concomitant medications should be recorded in the CRF including supportive care drugs (eg, antiemetic treatment and prophylaxis), and the drugs used to treat adverse events or chronic diseases, and non drug supportive interventions (eg, transfusions).

Concurrent anticancer therapy with agents other than axitinib and MK-3475 is not allowed. Medications intended solely for supportive care (ie, antiemetics, analgesics, megestrol acetate for anorexia) are allowed.

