### **9.6.3. Concomitant Medications/Follow-up Systemic Therapy**

All medications received during the treatment period will be considered as concomitant medications and will be coded by WHO medical dictionary. Patients who received concomitant medications will be listed. Follow-up systemic therapy for the primary diagnosis will be summarized by categories of follow-up therapy and will be listed for each patient as appropriate.

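### SAP 8.3.3.2 states the concomitant-medication stop-date rule backwards for patients with no lead-in; followed literally, it misclassifies drugs in their prior and concomitant listings

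*SAP*

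**What the plan says.** SAP Section 8.3.3.2, under the concomitant medications heading, sets two definitions.

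- **Previous** depends on the start date. For patients without a lead-in, medications whose start date is "prior to C1D1 (for patients with no lead-in period) are considered previous medication".
- **Concomitant** depends on the stop date or on continuing use. The sentence opens with "All ongoing medications at the end of study or medications with a stop date on or after lead-in D1 (for patients with a lead-in period" and closes, for the other patients, with "prior to C1D1 (for patients with no lead-in period) are considered concomitant medication".

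Overlap is allowed: "If a medication satisfies both the definition of previous and concomitant medication, it will be considered both previous and concomitant medication". Two kinds of output use the definitions: a count ("The number of subjects with any concomitant drug/non-drug treatment will be summarized") and separate listings of prior and concomitant treatment.

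Protocol Section 9.6.3 defines the class differently: "All medications received during the treatment period will be considered as concomitant medications". Protocol Section 5.4 sets the recording window; medications "will be recorded from 28 days prior to the start of study treatment and up to 28 days post the last dose of study treatment". On who lacks a lead-in, the pharmacokinetic paragraph of Protocol Section 3.1 says: "There will be no lead-in period for the remaining patients in the Dose Expansion Phase".

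**The concern.** The two branches of one sentence run in opposite directions. With a lead-in, a drug is concomitant if it stopped on or after the first dosing day. Without one, it is concomitant if it stopped before the first dosing day, which describes a drug the patient was no longer taking when treatment began. The sentence is complete, so this is not a redaction or an extraction fault, and nothing elsewhere in either document corrects it.

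At stake is whether the listings show what patients took alongside study treatment. Time-limited courses are expected here: Protocol Table 6 calls for corticosteroids followed by a taper for several immune-related events, and Protocol Section 5.4.6 restricts glucocorticoids to stated purposes. A concomitant listing is an obvious place to look for such courses.

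The error also follows trial phase. All Dose Finding patients have a lead-in and most expansion patients need not. SAP Section 8.3.3 pools patients treated at the MTD across both phases for secondary safety data, so patients on the same dose would be classified by opposite rules.

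**Working it through.** The plan gives no figure to reproduce on this point. The check applies the written rule to every type of record and then counts the patients it governs.

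**Step 1. Classification.** Take a patient with no lead-in and set C1D1 = day 1. The day numbers are illustrative.

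- Previous, as written: start < 1.
- Concomitant, as written: stop < 1, or ongoing at study end.
- Concomitant, using the lead-in branch's direction: stop ≥ 1, or ongoing at study end.

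| Pattern | Start, stop | As written | With stop on or after C1D1 |
|---|---|---|---|
| Stopped before treatment | −20, −5 | previous and concomitant | previous |
| Started before, stopped on treatment | −20, 30 | previous | previous and concomitant |
| Started before, stopped on C1D1 | −5, 1 | previous | previous and concomitant |
| Started and stopped on treatment | 60, 100 | neither | concomitant |
| Started before, ongoing at study end | −20, none | previous and concomitant | previous and concomitant |
| Started on treatment, ongoing at study end | 60, none | concomitant | concomitant |

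Four of the six patterns change class. The first does occur in the data, because recording begins 28 days before treatment. The fourth is the completed steroid taper: it meets neither definition and so appears in neither listing.

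**Step 2. Patients governed by the clause.** Inputs:

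- Expansion cohort: up to 40 (Protocol Summary, Sample Size Determination).
- Expansion patients with a lead-in: at least 8 (Protocol Section 3.1).
- Total enrolment: approximately 60 (Protocol Section 3.1).
- Dose Finding patients: all have a lead-in (Protocol Section 3.1), so none is affected.

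Maximum without a lead-in = 40 − 8 = 32. As shares: 32/40 = 80% of the expansion cohort and 32/60 ≈ 53% of all patients.

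**Step 3. Effect on the planned outputs.**

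- *Listings.* Each record of the first four patterns is misplaced or missing.
- *Count of subjects with any concomitant treatment.* A patient is wrongly lost only if all of that patient's on-treatment drugs were stopped before study end and no drug stopped before C1D1 brings the patient back in. A patient is wrongly gained only if a drug stopped before C1D1 is the sole qualifying record. One drug ongoing at study end keeps the patient counted under either rule.

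**The case against.** The strongest reply is that this is an evident drafting slip. The sentence just before it ends with the same C1D1 phrase, correctly, because there it applies to start dates. The lead-in branch and Protocol Section 9.6.3 both show the intent, and a programmer would probably query it. That explains the error but does not remove it. Protocol Section 9 lets the SAP modify the protocol's plans, so Section 9.6.3 does not automatically prevail. Code that departs from the text would be a deviation that SAP Section 2 says must be described in the study report.

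The reply is right about the consequences. A reader might infer that steroid and antihypertensive use would vanish from the safety summary. The documents do not support that:

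- No tabulation by drug or class is planned. The only concomitant summary is the any-treatment count.
- Antihypertensives still being taken at study end are kept. Protocol Table 5 has them added while axitinib continues, so many may be ongoing, though no figure is given.
- Drugs started before C1D1 and stopped on treatment still appear in the prior listing.
- All these drugs are still recorded on the CRF, so no data are lost.

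A reader might also take 32 as the number of patients with wrong output. It is a ceiling on patients governed by the clause.

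**Conclusion.** The rule is wrong as written, and the severity is minor. For patients with no lead-in it contradicts both its own lead-in branch and Protocol Section 9.6.3. It misclassifies any drug with a stop date before study end.

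The clause governs at most 32 patients, assuming the expansion cohort reaches its planned 40 and only the minimum 8 have a lead-in. The number whose output would change depends on their medication records and cannot be derived from the documents. The consequences also assume that the text is programmed literally.

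The effect stops at the two listings and possibly the one count. It does not reach the DLT endpoint, the MTD estimate, response, PFS, OS or the adverse-event summaries. PFS censoring uses subsequent anti-tumor treatment, defined separately in SAP Appendix 2. Surgery, radiation and follow-up systemic therapy have listings of their own. The safety outputs are descriptive throughout.

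**What to change.** In the concomitant-medication sentence of SAP Section 8.3.3.2, change the no-lead-in branch so that the stop date must fall on or after C1D1. Leave the lead-in branch (on or after lead-in D1) and the provision for drugs ongoing at study end as they are. The previous-medication sentence needs no change.

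The cost is a few words in the SAP and a matching line in the programming specification. No new data and no design change are needed.

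One small gap would remain in both branches. Recording runs to 28 days after the last dose, so a drug first started after treatment ended would still count as concomitant on stop date alone, while Protocol Section 9.6.3 speaks of the treatment period. The sponsor could settle that in the same edit by stating whether the class ends with the last dose or with the recording window.
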